7.7. Serious Adverse Event Reporting to Regulatory Authorities and study Investigators

Any new and unexpected AEs may be reported to the IRB or IEC as required by local Regulations.

Suspected unexpected serious adverse reactions (SUSARs) are AEs that are believed to be related to study drug and are both unexpected (i.e., the nature or severity is not expected from the information provided in the Investigator Brochure) and serious. SUSARs are subject to expedited reporting to the Regulatory Authorities and IRB & EC as appropriate.

Investigators will be notified by the Diamond PV Limited of all SAEs that require prompt submission to their Institutional Review Board (IRB) or Independent Ethics Committee (IEC). Investigators should provide written documentation of IRB/IEC notification for each report to the Sponsor or CRO. The Sponsor or CRO will ensure that the appropriate regulatory authorities are notified of all reportable SAEs.

8. DATA ANALYSIS AND STATISTICAL METHODS

8.1. Analysis Sets

Inclusion of subjects in the various analysis sets will be determined and documented prior to study unblinding.

The Screen Set will include all subjects who signed the informed consent.

The **Enrolled Set** will include all subjects who passed screening irrespective of whether they received study treatment.

Sponsor Project Nº CL-5937-02

The **Randomized Set** will include all subjects assigned a randomization number, irrespective of whether they go on to receive treatment. If this analysis set coincides with the intention-to-treat analysis set, it will be omitted.

The **Intention-to-treat (ITT) Set** will include all randomized subjects who take at least one dose of study medication and provide at least one baseline and at least one post-baseline cough frequency measurement. Analyses will be conducted by planned treatment. This analysis set will be the primary efficacy analysis set.

The **Per-Protocol (PP)** Set will be a subset of the ITT set who do not violate inclusion or exclusion criteria and/or deviate from the protocol, in a way that could influence their efficacy assessment. Consequently this analysis set will be used for sensitivity analyses of efficacy endpoints. Given the crossover design the inclusion in this set will consider each study period separately (i.e. a subject could be included in this set for one period but excluded from the other).

The **Safety Analysis (SAF) Set** will include all subjects who receive at least one dose of either BLU-5937 or placebo. Analyses will be conducted by treatment received.

The **Pharmacokinetic Set** will include all subjects in the SAF set who have at least one evaluable (i.e. not impacted by any important protocol deviations or other events) post-dose PK measurement (even if below the limit of quantification). Subjects will be analyzed according to the treatment received and dose taken.

8.2. General Approach

Full details of all planned analyses shall be specified in the SAP which will be finalized prior to database lock.

For continuous variables, the number of observations, mean, standard deviation, median, minimum and maximum shall be presented as appropriate. For categorical values, the number of observations and percentages shall be presented as appropriate.

Subject-level listings shall be provided to support all tabulated output.

8.3. Demographic Data and Other Baseline Characteristics

Disposition, demographic data (e.g. age, gender and race) and other baseline characteristics including medical and medication history shall be summarized.

8.4. Efficacy Analysis

8.4.1. Primary Endpoint – Awake Cough Count

The primary efficacy endpoint is change from baseline in awake cough count by dose level derived as follows:

Change in Awake Cough Count = Post-treatment Cough Count - Baseline Cough Count

Hence a negative result indicates a decrease in cough frequency while a positive result indicates an increase.

Due to the skewed nature of cough frequency data, awake cough frequency will be log transformed prior to analysis.

The baseline scores will be recorded on Day 0 (Visit 2) and Day 30 (Visit 8) for Periods 1 and 2 respectively.

If there are any zero cough frequencies within the data all values will have 0.1 added to their cough frequency (equates to 1 cough every 10 hours) prior to transforming the data.

Sponsor Project Nº CL-5937-02

A repeated measures mixed model analysis of variance will be used to evaluate the primary endpoint. The log transformed awake cough frequency measured at assessment visits within periods will be the repeated measure.

A repeated measure mixed model (MMRM) suitable for a crossover design with repeated measures within periods will be used. The fixed effects, random effects and repeated measure structure for the model will be as follows:

Fixed effects: Sequence (AB, BA), Period (1, 2), Treatment (BLU-5937, Placebo), Assessment Visit (1 to 4 within each period) and the Treatment by Assessment Visit interaction. Average baseline (average of the 2 period baselines) and period specific baselines will be included as covariates.

Random Effects: Subject

Repeated measures structure: the model will take account of the assessment visits within subject periods

Contrast statements will be used to compare each dose of active treatment against placebo at the corresponding assessment visits of the periods. The mean change from baseline (on the log scale), with associated standard errors will be presented for each treatment at each assessment visit. Treatment differences vs placebo with corresponding 95% CIs will also be presented for each dose. Means will be back-transformed to estimate the ratio of the visit to baseline for each treatment at each visit and the treatment differences will be back-transformed to estimate the ratio of the visit to baseline for the active group, adjusted for the placebo effect. All ratios will be accompanied by their 95% CIs and the p-values comparing active doses to placebo will be presented.

Geometric mean profile plots against day will be produced with asymmetric error bars (back-transformed from the log scale), with separate lines for each treatment.

The percent difference change between BLU-5937 doses and placebo will be estimated by 100 * e(diff - 1); where diff is the difference provided by the analysis of the log-transformed variable.

Using an MMRM analysis is suitable when assuming missing data is missing at random (MAR).

Alternative sensitivity analyses will be performed:

- the reasons for data being missing will be reviewed prior to unblinding the randomization. If the reason for missingness is deemed as being potentially related to lack of treatment response, the missing value will be imputed with the worst cough score (for that patient) recorded. If the subject withdraws prior to Period 2 their missing Period 2 data will not be imputed in this way. After imputation scores will be analysed using the methods described for the primary analysis.
- the primary analysis will be repeated using the PP analysis set.
- the primary analysis assumes that the data are log-normally distributed. An analysis will also be performed of the untransformed data. On this scale changes from baseline and differences with placebo for the changes from baseline will be estimated along with 95% confidence intervals.

8.4.2. Secondary Endpoints

The following secondary endpoints will be analysed using the ITT analysis set.

- Change from baseline in 24-hour cough frequency at end of each dose level and follow-up
- Change from baseline in awake cough frequency at follow up

Sponsor Project Nº CL-5937-02

- Change from baseline in cough severity as measured by the Visual Analogue Scale (VAS) at end of each dose level and follow-up
- Change from baseline in Leicester cough questionnaire (LCQ) total scores at end of each treatment period
- Global rating of change scale at end of each dose level and follow-up

Statistical approaches for analysis of the secondary endpoints will be detailed in the SAP and will be generally similar in approach to that of the primary endpoint. Only cough count data will be log transformed prior to analysis.

Global rating of change scale will be remapped and given scores to create a continuous endpoint. A lower score will be considered a more positive outcome.

8.4.3. Exploratory Efficacy Endpoints

The analyses of exploratory endpoints will be described in the statistical analysis plan.

Cough data will be log transformed prior to analysis and appropriately back transformed for presentation of results.

8.5. Multiplicity

No adjustment for multiplicity is required.

8.6. Extent of Exposure

Exposure data will be summarized by treatment group.

8.7. Safety Analysis

Adverse events will be classified into standardized medical terminology from the verbatim description (Investigator term) using the Medical Dictionary for Regulatory Activities (MedDRA). Adverse events will be presented by preferred term nested within System Organ Class. Verbatim description and all MedDRA level terms, including the lower level terms, for all AEs will be contained in the data listings of the CSR.

Adverse events will be summarized by presenting, for each treatment group, the incidence of AEs. Although a MedDRA term may be reported more than once for a subject, that subject will be counted only one time in the incidence count for that MedDRA term. In addition to presenting summaries by treatment group, AEs emergent from Days 1-4, Days 4-8, Days 8-12 and Days 12-16 will also be presented, with the break points being the start of dosing for each dose phase.

Only treatment-emergent adverse events (TEAEs) will be summarized. Adverse events that are not treatment-emergent will be listed. Treatment-emergent adverse events are defined as AEs that

- emerge during treatment, having been absent at pre-treatment (Baseline) or:
- re-emerge during treatment, having been present at Baseline but stopped prior to treatment, or
- worsen in severity during treatment relative to the pre-treatment state, when the AE is continuous

Taste disturbance AE's will also be presented and summarized.

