1.8. Study Rationale

With extensive efforts in animals, one P2X3 antagonist drug has started to validate the mechanism of P2X3 inhibition in cough hypersensitivity in clinical trials, gefapixant (AF-219, MK-7264). In 2014, a proof-of-concept phase II study highlighted a large decrease in cough frequency (75%) with gefapixant 600 mg BID vs placebo in 24 chronic cough patients (Abdulqawi, 2015). Follow-up studies exploring a wide range of doses have indicated a clear dose-response relationship between potent cough suppression and gefapixant administration, indicating promising potential for the P2X3 antagonist in being the first new cough therapy in 60 years.

However, gefapixant's attractive efficacy has been limited by unwanted taste side-effects (dysgeusia, hypogeusia or ageusia). Initial human proof-of-concept study at a high dose of 600 mg twice daily led to clinically significant taste disturbances in all patients that were associated with a 25% dropout rate (Abdulqawi, 2015). Titration to lower doses led to a decrease in the taste side-effects, although these ontarget issues could not be resolved as gefapixant still led to significant taste adverse events at effective doses for cough suppression (Sheridan, 2016). The incidence of taste adverse events reported with gefapixant at the predicted therapeutic dose of 50 mg BID was 81% (Smith, 2017). The taste adverse events associated with gefapixant is believed to be due to its low selectivity for P2X3 homotrimeric receptors (involved in cough) versus P2X2/3 heterotrimeric receptors (responsible for taste perception).

Accordingly, a potent, orally bioavailable small molecule antagonist of P2X3 that is highly selective for P2X3 homotrimers versus P2X2/3 heterotrimers such as BLU-5937 would hypothetically limit unwanted taste side-effects while being efficacious in the treatment of chronic cough.

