2.1. Primary Objective

The primary objective of this study is to assess the efficacy and safety of BLU-5937 for the treatment unexplained, refractory chronic cough.

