2.5. Exploratory Efficacy Endpoints

2.6. Safety Endpoints

- Adverse Event (AE) reporting
- Spontaneous taste disturbance AE reporting (subjects will complete a questionnaire on type, severity and duration of taste disturbance AEs)
- Vital signs
- ECG
- Clinical laboratory
- Physical exam

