8.12. PK/PD Relationship

The relationship between systemic concentrations of BLU-5937 and the following will be explored graphically:

- reductions in awake cough frequency
- taste disturbance AEs

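### The visible plan for taste disturbance AEs is descriptive only: section 8.7 uses no within-subject pairing and gives no BLU-5937 minus placebo difference or interval

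*Combined protocol and SAP*

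**What the plan says.** Section 1.8 cites an 81% incidence of taste AEs with another P2X3 antagonist at its predicted therapeutic dose. It argues that a more selective drug "would hypothetically limit unwanted taste side-effects while being efficacious in the treatment of chronic cough". Section 2.1 states: "The primary objective of this study is to assess the efficacy and safety of BLU-5937". Section 2.6 makes spontaneously reported taste AEs a safety endpoint, supported by a questionnaire. The synopsis also lists the relation of taste AEs to systemic exposure.

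The analysis is in sections 8.7 and 8.12:

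- For all AEs: "Adverse events will be summarized by presenting, for each treatment group, the incidence of AEs".
- By dose phase: "AEs emergent from Days 1-4, Days 4-8, Days 8-12 and Days 12-16 will also be presented".
- For taste: "Taste disturbance AE's will also be presented and summarized".
- For exposure, with taste AEs among the listed outcomes: "The relationship between systemic concentrations of BLU-5937 and the following will be explored graphically".

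Section 8.4.1, by contrast, gives awake cough frequency a difference from placebo with a 95% CI at each dose. Section 8.2 leaves full detail to a SAP to be finalized before database lock and requires subject-level listings. No separate SAP text is available, and section 6.4 (Evaluation of Taste Disturbance) appears in the contents list without visible text.

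**The concern.** The secondary objective is to choose doses for Phase 2b/3, which means weighing cough reduction against taste disturbance. The first has a planned estimate and interval at each dose. The second has percentages and plots.

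Two things are lost. First, a percentage without an interval can mislead in either direction: a small excess may look like a drug effect, and no events may look like proof of none. Second, each completer is observed on both treatments, but the two marginal percentages do not show whether the subjects affected on placebo are also affected on BLU-5937. If the comparison is built only after unblinding, the taste terms and the handling of one-period subjects would be chosen with the results in view.

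**Working it through.** **Inputs.** The synopsis plans about 68 randomized subjects to obtain 62 completers, so n = 62 pairs. The visible text gives no taste rate for BLU-5937 or placebo, and no figure for a taste comparison, so there is no plan figure to reproduce. All counts below are assumptions.

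**Notation.** a = affected on both treatments, b = BLU-5937 only, c = placebo only, d = neither.

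- Difference D = (b − c)/n.
- Exact McNemar p = 2 × P(X ≤ min(b, c)), with X binomial on b + c trials and probability 0.5.
- Interval: Newcombe hybrid score for paired proportions. Lower limit = D − √[(p1 − l1)² − 2φ(p1 − l1)(u2 − p2) + (u2 − p2)²], where p1 and p2 are the incidences on BLU-5937 and placebo, l and u are Wilson limits and φ is the paired correlation (continuity-corrected when positive). The upper limit mirrors it.

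**Step 1: the same margins support different readings.** Take 9/62 (14.5%) against 3/62 (4.8%), so D = 6/62 = 9.7 points.

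| a | b | c | 95% CI (points) | McNemar p |
|---|---|---|---|---|
| 0 | 9 | 3 | −1.6 to 21.2 | 0.146 |
| 1 | 8 | 2 | −1.0 to 20.9 | 0.109 |
| 2 | 7 | 1 | 0.2 to 20.2 | 0.070 |
| 3 | 6 | 0 | 1.5 to 19.5 | 0.031 |

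As a check on the last row, p = 2 × 0.5⁶ = 0.031. The planned table would be identical in all four rows.

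**Step 2: range of differences against 3/62 on placebo.**

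| BLU-5937 | D (points) | CI if a = 0 | CI if a = 3 | p range |
|---|---|---|---|---|
| 3/62 | 0.0 | −9.2 to 9.2 | −6.1 to 6.1 | 1 |
| 6/62 | 4.8 | −5.4 to 15.4 | −2.2 to 13.3 | 0.51 to 0.25 |
| 12/62 | 14.5 | 2.3 to 26.8 | 5.3 to 25.3 | 0.035 to 0.004 |
| 15/62 | 19.4 | 6.3 to 32.1 | 9.1 to 30.7 | 0.008 to 0.0005 |

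From 12 against 3 upward, every pairing gives p < 0.05 and an interval above zero.

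**Step 3: what pairing buys.** Take 7 against 2 with one subject on both, so b = 6 and c = 1.

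- D = 5/62 = 8.1 points.
- Paired SE = √(7 − 25/62)/62 = 4.1 points. Unpaired SE = √(0.113 × 0.887/62 + 0.032 × 0.968/62) = 4.6 points.
- p = 2 × (1 + 7)/2⁷ = 0.125.
- The Wald interval is −0.1 to 16.2; the Tango score interval is −0.4 to 18.3.

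The gain in precision is small. The larger omission is the difference and its interval.

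**Step 4: single percentages.** The Clopper-Pearson upper limit for 0/62 is 1 − 0.025^(1/62) = 5.8%. For 6/62 (9.7%) the interval is 3.6% to 19.9%.

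**Step 5: what the fix can resolve.** With 5% on placebo and 62 pairs, exact McNemar power at the 0.05 level is 0.34 to 0.42 for 15% on BLU-5937, 0.64 to 0.72 for 20%, and 0.86 to 0.90 for 25%. Each range runs from independent responses to half of the placebo-affected subjects being affected on both.

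**Step 6: dose windows.** The windows in section 8.7 share Days 4, 8 and 12. Table 3 has the dose levels on Days 1–4, 5–8, 9–12 and 13–16, and section 8.7 itself sets the break points at the start of dosing for each phase. An AE starting on Day 4, 8 or 12 can therefore fall in two windows.

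**The case against.** The strongest case is that descriptive AE reporting suits an early Phase 2 trial meant to gather initial safety and efficacy data, with no taste hypothesis or margin. The plan also has dose windows, exposure plots, a questionnaire and subject-level listings, and an effect near the 81% cited for the other drug would be obvious from percentages. All of that stands. It bears on how much the gap matters, but none of it supplies a difference from placebo with an interval.

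A reader might infer that the trial cannot say whether BLU-5937 differs from placebo on taste. The documents do not support that. Completers receive both treatments, and listings let the pairs be rebuilt, so the gap lies in the planned analysis and not in the design.

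A reader might also infer that no taste comparison exists anywhere in the sponsor's plans. That cannot be shown, because section 6.4 and the deferred SAP are not visible.

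A further objection concerns the remedy. A paired estimate pooled over doses and restricted to subjects treated in both periods would drop anyone who left in Period 1, possibly because of taste. The planned loss is 68 − 62 = 6 subjects (8.8%), and section 1.8 links taste disturbance to a 25% dropout rate with the other drug. Such an estimate would also ignore period effects and could not inform dose choice. This objection stands and shapes the fix.

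**Conclusion.** The concern holds as a gap in the planned analysis. In the visible text, taste AEs are summarized by treatment and dose window and plotted against exposure. No within-subject table, difference from placebo or interval is planned. Under the assumed counts, differences of about 5 to 10 points over a placebo rate near 5% cannot be read from marginal percentages, while differences of about 15 points or more are distinguishable under every pairing.

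This rests on 62 pairs, on assumed taste rates, and on the absence of the analysis from the text that can be seen. Even after the fix, a 10-point difference would probably remain inconclusive (power at most about 0.42), so the aim is estimation, not a test. It is a cheap improvement that should be made, and it does not threaten the trial's validity.

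**What to change.** In section 8.7 or the SAP, fix a list of taste preferred terms before unblinding and report, overall and by dose window:

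1. Incidence on each treatment among all treated subjects (SAF set), with exact 95% CIs.
2. The four-way table (both, BLU-5937 only, placebo only, neither) for subjects treated in both periods, with the paired risk difference and a 95% score CI. Exact McNemar can be given as support.
3. A sensitivity estimate that keeps one-period subjects and adjusts for period, such as a GEE or mixed logistic model. Mainland-Gart can provide the period adjustment among pairs.

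State how taste AEs that persist across dose windows or into the washout are counted, and label all results as estimates without multiplicity control. Before attributing taste AEs to a dose level, reconcile the overlapping windows in section 8.7 with the dosing days in Table 3.

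The cost is a short addition to the text and one more table, with no new data. The downside is wide intervals, especially by dose window, where events will be fewer. If the SAP or section 6.4 already contains these items, only the cross-reference and the window definitions need attention.

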- K: For Women of Childbearing Potential
- L: Completed only if taste AEs are reported
- M: Subjects who test positive may be re-tested if consumed poppy seeds on bread products
- N: To be completed before morning dose
- O: Visit 8/Day 30 only
- P: Visit 9/Day 31 only.

[Randomization] * triggers shipment of additional treatment kits to the site.

[Randomization] **At visit 3/Day 1 if not already completed;

[Initial shipment of IP to a site is triggered once the first subject has started screening].

Version 5.0 (26/SEP/2019) Page **20** of **68**

INVESTIGATOR AND STUDY ADMINISTRATIVE STRUCTURE

Sponsor Project Nº CL-5937-02

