2.2. Secondary Objective

The secondary objective is to establish the optimal therapeutic doses for the Phase 2b/3 studies.

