3. STUDY DESIGN

This is a Phase 2, multicentre, randomized, double-blind, placebo-controlled, two-period crossover, dose escalation study of BLU-5937 in subjects with unexplained or refractory chronic cough.

Subjects will be screened during a period of up to 14 days and undergo a screening 24-cough monitoring using an objective measure of coughs (VitaloJAK Vitalograph, Ltd.) to exclude the mild cougher subjects (< 10 cough/hr, from awake cough count).

Approximately 68 subjects who meet entry criteria will be randomized into the study. There will be two 16-day treatment periods (BLU-5937 or placebo) with a 10-14 days washout period between treatment periods. Each Period will consist of 4 escalating dose levels. Each dose level will be of 4 days duration.

The duration of treatment for each subject is as follows:

Screening Period: up to 14 days

Sponsor Project Nº CL-5937-02

- Baseline Period 1: 1 day
- Treatment Period 1 (BLU-5937 or Placebo):
 16 days (escalating doses of 25, 50, 100, 200 mg BID or placebo; 4 days for each dose)
- Washout: 10-14 days
- Baseline Period 2: 1 day
- Treatment Period 2 (Placebo or BLU-5937):
 16 days (escalating doses of 25, 50, 100, 200 mg BID or placebo; 4 days for each dose)
- Follow-Up Period: 10-14 days

Individual subject participation is expected to be approximately 74 days including Screening, Baseline, Treatment periods and Follow-Up period.

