5.2. Investigational Product Management

5.2.1. Packaging, Labelling and Dispensing

The sponsor will be responsible for ensuring that the investigational product and placebo are manufactured in accordance with applicable current Good Manufacturing Practice (cGMP) regulations and requirements.

^{*} Alginate therapy is accepted but should not be taken concomitantly with study medication which should be taken an hour before or 2 hours after alginate.

[§] Stopping chronic corticosteroid use should be approved and supervised by a physician before stopping

Sponsor Project Nº CL-5937-02

The investigational product and placebo will be labelled according to the requirements of local law and legislation.

BLU-5937 tablets or placebo will be provided for Period 1 and 2 by in treatment kits containing 4 opaque HDPE bottles per kit for each period. Each bottle represents one of 4 dose levels (25, 50, 100, 200 mg BID). The investigational product will be administered as 25 mg tablets (for the 25, 50, 100 mg BID dose levels) or 200 mg tablets (for the 200 mg BID dose level) or matching placebos. BID dosing means every 12 hours, +/- approximately 1 hour. Each bottle will contain sufficient medication to cover the 4 -day treatment duration plus 1 extra day (total 5 days). When a new dose is dispensed it is to be started the following morning after the cough recording device is removed. There is no flexibility in visit window for Treatment visits; each dose is to be taken for 4 days.

Table:	3.	Treatment Kit Dispensing
I UDIC	•	Treatment the Dispensing

Study DayNo.#	BLU-5937 Dose*/Placebo	
Period 1 (treatment kit dispensing)		
Days 1-4	25 mg (1 tablet) BID or placebo	
Days 5-8	50 mg (2 tablets) BID or placebo	
Days 9-12	100 mg (4 tablets) BID or placebo	
Days 13-16	200 mg (1 tablet) BID or placebo	
Washout 10-14 days		
Day 17-30	No treatment	
Period 2 (treatment kit dispensing)		
Days 31-34	25 mg (1 tablet) BID or placebo	
Days 35-38	50 mg (2 tablets) BID or placebo	
Days 39-42	100 mg (4 tablets) BID or placebo	
Days 43-46	200 mg (1 tablet) BID or placebo	

^{*}Product can be administered without regard to meals

Once it is confirmed the subject has provided written consent and meets all the inclusion and none of the exclusion criteria the investigational product and placebo will be dispensed to individual subjects as per the randomization schedule.

Further details regarding packaging, labelling and accountability can be found in the pharmacy manual.

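### The by-dose AE table in section 8.7 counts onsets only, so AEs that persist through the escalation are missing from the higher-dose windows

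*Combined protocol and SAP*

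**What the plan says.** Section 3 fixes the escalation: "Each Period will consist of 4 escalating dose levels. Each dose level will be of 4 days duration". Table 3 shows the levels running 25, 50, 100, 200 mg BID with no drug-free days inside a period. Section 2.2 states: "The secondary objective is to establish the optimal therapeutic doses for the Phase 2b/3 studies".

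Section 8.7 first describes AE incidence by treatment group; for a term reported more than once, "that subject will be counted only one time in the incidence count for that MedDRA term". It then adds the only by-dose AE output it describes: "AEs emergent from Days 1-4, Days 4-8, Days 8-12 and Days 12-16 will also be presented". A clause that follows places each cut where dosing at the next level begins. Only treatment-emergent AEs are summarised. Each of the three routes to being emergent looks back to the state before treatment; the third is to "worsen in severity during treatment relative to the pre-treatment state, when the AE is continuous". The section closes by promising a summary of taste AEs, without a method.

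The section names no table of AEs ongoing at a dose level, no table of severity by level, and no rule for an AE that changes grade between levels. Elsewhere, the Synopsis promises safety summaries by dose and timepoint where suitable, section 8.12 plots taste AEs against plasma concentration, and section 8.2 leaves full detail to the SAP. The public document contains no separate SAP text.

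**The concern.** The trial is meant to inform dose choice, and section 1.8 rests the case for the drug on limiting taste effects. Under section 8.4.1, cough at each dose is compared with placebo at the corresponding visit, so it describes the subject's state at that dose. The by-dose AE table describes something else: who first became affected during those days.

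In a parallel dose-ranging trial the difference would matter less, because each subject has one dose. Here the same subjects carry their AEs upward. A subject whose taste AE began at 50 mg and is still present at 200 mg would appear in the 50 mg window and not in the 200 mg window. A reader who sets the cough result at 200 mg beside the 200 mg AE row would be comparing a state with a count of new events, and could take the higher dose to be better tolerated than it was.

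**Working it through.** The plan gives no figure to reproduce here. The check is a reading of the counting rule, then an illustration of its effect.

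**Step 1: where a persisting AE goes.** An AE enters a window by emerging in it. Emergence is relative to pre-treatment, and nothing resets it at a dose step. An AE that begins in window k and continues therefore belongs to window k only.

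**Step 2: basic arithmetic.** Assume that AEs, once present, last to the end of the period. The onset share at each level is then the difference between successive shares affected. For an assumed 10/20/35/50% affected:

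- 25 mg: 10%
- 50 mg: 20 − 10 = 10%
- 100 mg: 35 − 20 = 15%
- 200 mg: 50 − 35 = 15%

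The table prints 15% at 200 mg when 50% are affected.

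**Step 3: range over persistence.** Inputs: N = 62, the planned completers (Synopsis), all taken as dosed at every level. Onset shares o_k and persistence q from one level to the next are assumed, and resolved AEs are taken not to recur. Onset count = N × o_k. Number affected = N × c_k, with c_k = q × c_(k−1) + o_k. Entries are subjects at 25/50/100/200 mg.

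| Assumed onset | Onset table | Affected, q = 1 | Affected, q = 0.75 | Affected, q = 0.5 |
|---|---|---|---|---|
| 20/10/5/5% | 12.4/6.2/3.1/3.1 | 12.4/18.6/21.7/24.8 | 12.4/15.5/14.7/14.1 | 12.4/12.4/9.3/7.8 |
| 10% at each level | 6.2/6.2/6.2/6.2 | 6.2/12.4/18.6/24.8 | 6.2/10.9/14.3/17.0 | 6.2/9.3/10.9/11.6 |
| 5/5/10/20% | 3.1/3.1/6.2/12.4 | 3.1/6.2/12.4/24.8 | 3.1/5.4/10.3/20.1 | 3.1/4.7/8.5/16.7 |

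With q = 0 the number affected equals the onset count in every row.

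At 200 mg the undercount under q = 1 is 24.8/3.1 = 8-fold, 24.8/6.2 = 4-fold and 24.8/12.4 = 2-fold. Under q = 0.5 it is about 2.5-, 1.9- and 1.3-fold. In the first row with q = 1, the onset table falls while the number affected rises. In the third row the dose ordering is kept.

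**Step 4: can the reader add up the onset rows?** With q = 1, yes: 12.4 + 6.2 + 3.1 + 3.1 = 24.8, the number affected at 200 mg. With q = 0.5 the same sum is still 24.8, but only 7.8 are affected. The onset row and the cumulated rows bracket the answer (3.1 to 24.8) without locating it, and neither gives severity by level.

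**Step 5: the window labels.** Days 1-4, 4-8, 8-12 and 12-16 cover 4 + 5 + 5 + 5 = 19 day-slots for 16 days; Days 4, 8 and 12 each fall in two windows. Section 5.2.1 says: "When a new dose is dispensed it is to be started the following morning after the cough recording device is removed". Table 3 accordingly has Days 5-8, 9-12 and 13-16. The start-of-dosing clause in section 8.7 agrees with Table 3, but its labels do not. Days 4, 8 and 12 are also visit days on which AEs are recorded. Period 2 (Days 31-46 in Table 3) has no windows stated.

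**The case against.** The case on the other side has several good points.

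- **Onset incidence by phase is a valid measure.** It answers which dose step brings new events. A present-at-level count has its own weakness: an AE that began at 25 mg is counted again at each later level, so dose is mixed with time on drug and carry-over. This stands. It is a reason to show both tables, not to omit one.
- **Other taste outputs are planned.** A reader might infer that taste is measured only as new onsets. The documents do not support that. Section 2.6 makes a questionnaire on the type, severity and duration of taste AEs a safety endpoint, section 8.7 promises a separate taste summary, and section 8.12 plots taste AEs against concentration. Section 6.4, on evaluating taste disturbance, is listed in the contents but is not visible in the public copy. None of the visible text, however, says how an ongoing AE is assigned to a dose.
- **Some tempting readings go past the text.** A persisting AE is charged to its onset dose, which is the lowest dose only if it began on Days 1-4. The worsening criterion defines what is treatment-emergent. It does not say that a rise in grade between levels creates no new event; the text is silent, and section 7.6 covers only an AE that becomes serious. Section 8.7 does not say whether once-per-term counting applies within or across windows, and gives no window denominators.
- **The rates are assumed.** This stands. The 81% taste incidence in section 1.8 belongs to a different drug, at a single dose, and cannot be spread over the four levels of this one.

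**Conclusion.** The point holds in limited form. The only by-dose AE table described is by onset, and under forced ascending dosing without gaps it leaves persisting AEs out of the later windows. It is therefore incomplete and can understate the number of subjects affected at higher doses.

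How much depends on persistence, which the documents do not give for this drug. There is no distortion if AEs resolve within their 4-day level. In the illustrations the undercount at 200 mg runs from about 1.3-fold (half persisting, rising onset) to 8-fold (full persistence, front-loaded onset). These figures rest on assumed onset and persistence rates, a constant 62 subjects and no recurrence.

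It would be too strong to say that the plan yields a wrong tolerability profile or a wrong dose choice. No document says that dose selection will rest on this table alone, and the deferred SAP detail could still supply what is missing. This is a cheap improvement that supports a stated objective.

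**What to change.** In section 8.7 and the SAP:

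1. Keep the onset table. Add, at least for taste AEs, a table of subjects with the AE new or ongoing at each dose level, with the worst severity recorded in that level where available. Use subjects dosed at that level as denominator, and show BLU-5937 beside the matched placebo days of the other period.
2. State that once-per-term counting applies within each level, and say how an AE that worsens from one level to the next is counted.
3. Use the same present-at-level variable in the section 8.12 taste plots, and read both tables together for any by-dose tolerability statement.
4. Reconcile the window labels with the dosing days in Table 3, and add the Period 2 days. Because the washout may be 10 to 14 days or longer, counting days from the first dose of each period would serve both periods.

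The cost is SAP wording and one table built from AE and taste data already planned. One check is needed: under Table 1, footnote L, the taste questionnaire is "Completed only if taste AEs are reported". The visible text does not say that it is repeated at each level while a taste AE continues, so severity by level may be incomplete unless that is confirmed. The downsides are that higher-dose percentages may look less favourable, and that the added count mixes dose with time on drug and carry-over from lower doses. A table footnote should say so.
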